### 2.2.2 Secondary objective(s)

- **Safety**
  - To determine the long-term safety of bivalent GI.1/GII.4 norovirus vaccine through 12 months after the last vaccination.
- **Immunogenicity**
  - To assess the long-term immunogenicity of oral bivalent GI.1/GII.4 norovirus vaccine administration in healthy lactating female participants and most critically, the association with vaccine specific antibody responses in breast milk.

### 2.2.3 Exploratory objective(s)

- **Immunogenicity**
  - To determine the additional immunogenicity parameters of bivalent GI.1/GII.4 norovirus vaccine including immunogenicity response in breastfed infants.
  - To determine the clinical effects in subjects presenting with acute gastroenteritis symptoms during the study period.

## 2.3 Endpoints

### 2.3.1 Primary endpoints

- **Safety:**
  - Frequency, duration, and severity of solicited symptoms of reactogenicity (local, systemic) for 1 week following each dose of study drug.
  - Frequency, duration, and severity of unsolicited treatment-emergent adverse events (TEAEs), serious AEs (SAEs), adverse events of special interest (AESIs), and new onset of chronic illness (NOCIs) through the active period (4 weeks post last dose).
- **Immunogenicity:**
  - Serum VP1 specific (GI.1 and GII.4) IgA through the active period measured by Meso Scale Discovery (MSD) assay by dose level
    - Geometric mean concentration (GMC) at Day 1, Day 8 and Day 29
    - Geometric mean fold rise (GMFR) from Day 1 to Day 8 and from Day 1 to Day 29
    - The number of subjects in each dose group that had a 2-fold, 3-fold and 4-fold GMC rise or greater in serum VP1 specific IgA (GI.1 and GII.4) between Day 1 and any other timepoint.
  - Breast Milk VPI specific (GI.1 and GII.4) IgA through the active period measured by Meso Scale Discovery (MSD) assay by dose level
    - Geometric mean concentration (GMC) at Day 1, Day 8, and Day 29
    - Geometric mean fold rise (GMFR) from Day 1 to Day 8, and from Day 1 to Day 29

- The number of subjects in each dose group that had a 2-fold, 3-fold and 4-fold GMC rise or greater in breast milk VP1 specific IgA (GI.1 and GII.4) between Day 1 and any other timepoint.

### 2.3.2 Secondary endpoints

- **Safety**
  - Frequency, duration, and severity of all SAEs, AESIs, and NOCIs through 12 months after last study drug dose
- **Immunogenicity**
  - Serum VP1 specific (GI.1 and GII.4) IgA through 6 months after study drug dose measured by Meso Scale Discovery (MSD) by dose level
    - Geometric mean concentration (GMC) at Day 180
    - Geometric mean fold rise (GMFR) from Day 1 to Day 180
    - The number of subjects in each dose group that had a 2-fold, 3-fold and 4-fold GMC rise or greater in serum VP1 specific IgA (GI.1 and GII.4) between Day 1 and Day 180.
  - Breast Milk VP1 specific (GI.1 and GII.4) IgA through 6 months after study drug dose measured by Meso Scale Discovery (MSD) by dose level
    - Geometric mean concentration (GMC) at Day 60 and Day 180
    - Geometric mean fold rise (GMFR) from Day 1 to Day 60 and from Day 1 to Day 180
  - Serum VP1 specific (GI.1 and GII.4) IgG through 6 months after study drug dose measured by Meso Scale Discovery (MSD) by dose level
    - Geometric mean concentration (GMC) at Day 1, Day 8, Day 29, and Day 180
    - Geometric mean fold rise (GMFR) from Day 1 to Day 8, from Day 1 to Day 29, and from Day 1 to Day 180
    - The number of subjects in each dose group that had a 2-fold, 3-fold and 4-fold GMC rise or greater in serum VP1 specific IgG (GI.1 and GII.4) between Day 1 and any other timepoint.
  - Serum Blocking titers 50 (BT50) (GI.1 and GII.4) through 6 months after study drug dose measured by Histo-blood group antigen (HBGA) assay by dose level
    - Geometric mean titer (GMT) at Day 1 and Day 29
    - Geometric mean fold rise (GMFR) from Day 1 to Day 29,
    - The number of subjects in each dose group that had a 2-fold, 3-fold and 4-fold GMT rise or greater in serum blocking titers 50 (BT50) (GI.1 and GII.4) between Day 1 and any other timepoint.

### 2.3.3 Exploratory endpoints

- **Efficacy:**
  - Occurrence of norovirus acute gastroenteritis
- **Immunogenicity:**
  - Saliva VP1 specific (GI.1 and GII.4) IgA from lactating mother measured by MSD by dose level
    - Geometric mean concentration (GMC) at Day 1, Day 8, Day 29, Day 60 and Day 180

- Geometric mean fold rise (GMFR) from Day 1 to Day 8, from Day 1 to Day 29, from Day 1 to Day 60, and from Day 1 to Day 180
- Nasal VP1 specific (GI.1 and GII.4) IgA from lactating mother measured by Meso Scale Discovery (MSD) by dose level
  - Geometric mean concentration (GMC) at Day 1, Day 8, Day 29, Day 60 and Day 180
  - Geometric mean fold rise (GMFR) from Day 1 to Day 8, from Day 1 to Day 29, from Day 1 to Day 60, and from Day 1 to Day 180
- Infant stool VP1 specific (GI.1 and GII.4) IgA measured by Meso Scale Discovery (MSD) by dose level
  - Geometric mean concentration (GMC) Day 1, Day 29, and Day 60
  - Geometric mean fold rise (GMFR) from Day 1 to Day 29 and from Day 1 to Day 60
- Breast Milk Antibody blocking titers 50 (BT50) (GI.1 and GII.4) measured by BT50 assay by dose level
  - Individual subject titers on samples and some timepoints that have a high likelihood of success, assuming the assay works in breast milk samples
- Breast Milk neutralizing antibody titers (GI.1 and GII.4) measured by norovirus human intestinal enteroid model.
  - Individual subject titers on samples and sometime points that have a high likelihood of success, under the assumption that the assay works in breast milk samples. At the date of this protocol, only serum GII.4 neutralizing antibodies have been successfully measured.

## 2.4 Sample Size

A sample size of 76 randomized subjects (30 each in medium and high dose levels and 16 in placebo) is not based on formal statistical testing but rather based on clinical judgement and predicted to yield meaningful safety and immunogenicity results. Placebo was added for safety comparison.

## 2.5 Randomization

Assignment of a Subject Number:

New subjects once deemed eligible and enrolled in the study will also receive a randomization number and treatment assignment, based on the blinded randomization schedule. The subject number will be used as the primary identifier for the complete duration of the study. After the subject signs the informed consent form (ICF), the Investigator (or designee) will enter the subject into the Screening Log, once randomized or screen failed their data will be entered into the eCRF.

Randomization:

After signing an informed consent, the subjects will undergo screening assessments to determine study eligibility over a 45-day Screening Period. All subjects who sign a study specific informed consent form will have data entered into the EDC. On Day 1, subjects will be randomized in a 30:30:16 ratio to one of the three treatment arms to receive active vaccine or placebo as follows (Table 2).

**Table 2: Study Arms**

Arm Title*	Arm 1	Arm 2	Arm 3
Arm Description	Medium Dose Bivalent GII.4/GI.1 vaccine	High Dose Bivalent GII.4/GI.1 vaccine	Placebo
Per Strain Dose (IU) +/-0.5 log	5×10 	1×10 	N/A
Total Dose (IU/dose)	1×10 	2×10 	N/A

### 3. STATISTICAL CONSIDERATIONS

Data will be handled and processed per the sponsor's representative (██████) Standard Operating Procedures (SOPs) and guidelines, which are written based on the principles of good clinical practice (GCP) E6.

#### 3.1 General Considerations

All data collected on the electronic case report form (eCRF) will be presented in the data listings and will be sorted by treatment arm, subject number and visit, where applicable. All descriptive summaries will be presented by treatment arm and nominal visit.

All safety and immunogenicity descriptive summaries will be presented by treatment arm and nominal visit.

Unless otherwise stated, the following methods will be applied:

- Continuous variables: Descriptive statistics will include the number of non-missing values (n), arithmetic mean, standard deviation (SD), median, minimum and maximum values.

The minimum and maximum values will be displayed to the same decimal precision as the source data, the arithmetic mean, SD and median values will be displayed to one more decimal than the source data for the specific variable.

95% Confidence Intervals (CIs), mean differences (among treatments and from baseline) and least-square (LS-Means) values will be displayed to one more decimal than the source data for a specific variable. P-values will be displayed to 3 decimal places.

The appropriate precision for derived variables will be determined based on the precision of the data on which the derivations are based, and statistics will be presented in accordance with the above-mentioned rules.

- Categorical variables: Descriptive statistics will include counts and percentages per category. The denominator in all percentage calculations will be the number of subjects in the relevant analysis population with non-missing data, unless specifically stated otherwise. Percentages will be displayed to one decimal place. Proportions will be displayed to 3 decimal places.

95% Confidence Intervals (CIs), difference in proportions and other categorical parameters will be displayed to one decimal place for percentages. Proportions will be displayed to 3 decimal places. p-values will be displayed to 3 decimal places.

- Repeat/unscheduled assessments: Only values collected at scheduled study days/time points will be presented in summary tables. If a repeat assessment was performed, the result from the original assessment will be presented as the result at the specific visit/time point. All collected data will be included in the data listings.
- Assessment windows: All assessments will be included in the data listings and no visit windows will be applied to exclude assessments that were performed outside of the protocol specified procedure windows.
- Result display convention: Results will be center aligned in all summary tables and listings. Subject identifiers visit and parameter labels may be left-aligned if required.
- Date and time display conventions: The following display conventions will be applied in all outputs where dates and/or times are displayed:

Date only: YYYY-MM-DD

Date and time: YYYY-MM-DD HH:MM

If only partial information is available, unknown components of the date or time will be presented as 'NK' (not known), i.e., '2016-NK-NK'. Times will be reported in military time.

### 3.2 Key Definitions

The following definitions will be used:

- **Baseline:** The baseline value is defined as the last available valid (quantifiable continuous or categorical value), non-missing observation for each subject prior to vaccine administration. The mean will be chosen for continuous variables. Repeat and unscheduled assessments will be included in the derivation of the baseline values.
- **Change from Baseline:** The change from baseline value is defined as the difference between the result collected/derived at a post-baseline visit/time point and the baseline value and will be calculated for all continuous parameters using the following formula:

$$\text{Change from Baseline Value} = \text{Result at Visit/Time Point} - \text{Baseline Value}$$

The change from baseline value will only be calculated if the specific post-baseline visit/time point result and the baseline value for the parameter are both available and will be treated as missing otherwise.

- **Fold Change from Baseline:** The fold change from baseline value is defined as the post baseline value divided by baseline value in original scale and point will be calculated for all continuous parameters using the following formula:

$$\text{Fold Change from Baseline Value} = \text{Post Baseline Result (in original scale)} / \text{Baseline Value (in original scale)} \text{ if the baseline value is not equal to zero or missing.}$$

- **Study day:** The study day of an event is defined as the relative day of the event starting with the date of the first study drug administration (reference date) as Day 1 (there will be no Day 0).

The study day of events occurring before the first study drug administration will be calculated as:

$$\text{Study Day} = (\text{Date of Event} - \text{Date of First Study Drug Administration})$$

For events occurring on or after Day 1, study day will be calculated as:

$$\text{Study Day} = (\text{Date of Event} - \text{Date of First Study Drug Administration}) + 1$$

Study days will only be calculated for events with complete dates and will be undefined for events that are 'Ongoing' at the end of the study.

Relative days compared to an alternative reference point will be calculated similarly, but the alternative starting reference start date will be used instead of the date of the first study drug dosing.

- **Prior Medications:** Prior medications are defined as any medication where the use was stopped prior to the first administration of the study medication.
- **Concomitant Medications:** Concomitant medications are defined as any medication (other than the study vaccine) that was used at least once after the first administration of the study drug. Medications that were stopped on the same date as the first study drug administration will be defined as concomitant medications. If a clear determination cannot be made (partial medication end dates) the medication will be classified as concomitant
- **Treatment Emergent Adverse Events (TEAEs)** are defined as adverse events, that began after the start of an investigational product or an already present event that worsens either in intensity or frequency following the intervention.
- **Duration of Adverse Events (AE) (days)** is defined as: AE end date - onset of AE + 1.

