### **3.5 Handling of Missing Data**

All collected and derived data will be included in the subject data listings. No imputations will be made for missing or incomplete data unless otherwise stated.

For the classification of Treatment emergent adverse event (TEAE) and Concomitant medication, the following will be applied in the following order:

- a. If all dates/times (start and stop) are missing, the event/medication will automatically be classified as a TEAE/Concomitant medication.
- b. For AEs with a missing start date/time, if the event end date/time is prior to first study drug administration, the event will not be classified as a TEAE.
- c. If only the AE start year/ medication end year is present and is the same or is after the first study drug administration year unit, the event/medication will be classified as a TEAE/Concomitant medication.
- d. If the AE start month and year/medication end month and year are present and are the same or after the first study drug administration month and year units, the event/medication will be classified as a TEAE/Concomitant medication.

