#### 13.2 Unsolicited AE from Day 1 to Day 29 Post-Vaccination

An unsolicited AE is an observed AE that does not fulfill the conditions prelisted in the eCRF in terms of diagnosis and/or onset window post-vaccination; this also includes progression of chronic diseases. Unsolicited AEs includes both serious (SAEs) and non-serious unsolicited AE.

The unsolicited AE summaries will include:

- Overall summary of Unsolicited TEAEs that included at least one:
  - Unsolicited TEAEs

- Grade  $\geq 3$  Unsolicited TEAEs
- Related Unsolicited TEAEs
- Grade  $\geq 3$  and Related Unsolicited TEAEs
- Serious TEAE
- Adverse Events of Special Interest (AESIs)
- New Onsets of Chronic Illness (NOCIs)
- Unsolicited TEAEs lead to study discontinuation
- Unsolicited TEAEs result in death
- Unsolicited TEAEs summary by SOC and PT
- Grade  $\geq 3$  Unsolicited TEAEs summary by SOC and PT
- Related Unsolicited TEAEs summary by SOC and PT

The Grading of Severity of an TEAE is defined as:

- Grade 1 = mild
- Grade 2 = moderate
- Grade 3 = severe +/- life threatening

In the summary tables, the total number of subjects having reported at least one unsolicited AE with the proportion and the associated Clopper-Pearson 95% CIs, as well as the total number of AEs reported and the duration will be provided for each treatment arm. For example, the tables will state that X (%) subjects have reported Y events in the treatment arm A. Then, they will present the details of unsolicited AEs per SOC and PT with the same information: number (%) of subjects and number of events.

In the summary tables, unsolicited AEs will be presented by decreasing frequency of number of subjects with event and total events under “overall” treatment arm within each SOC and then similarly by decreasing frequency of number of subjects with event and total events under “overall” treatment arm within each PT.

Missing unsolicited TEAE dates will be handled according to the rules determined in [section 3.1](#) (Date and time display conventions)

In addition, the duration of unsolicited TEAEs will be evaluated descriptively where subjects without AE are counted as missing.

All the unsolicited AEs collected during the active period of the study will also be provided for each treatment arm, study day, by severity and relationship to the treatment in by-subject listings. Separate listings will be done for subjects with TEAEs leading to study discontinuation, SAEs, AESIs, NOCIs and for Death events.

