### **13.4 New Onset of Chronic Illness**

New Onset of Chronic Illness (NOCI) is defined as diagnosis post-enrollment and vaccination of a new medical condition which is chronic in nature, including those potentially controllable by medication (e.g., diabetes, asthma).

In the summary tables, the total number of subjects having reported at least one NOCI with the proportion and the total number of NOCIs reported will be provided for each treatment arm. For example, the tables will state that X (%) subjects have reported Y events in treatment arm A. Then, they will present the details of NOCIs per SOC and PT with the same information: number (%) of subjects and number of events.

The NOCIs summaries at Day 365 Post-Vaccination will include:

- NOCIs summary by SOC and PT
- NOCIs summary by SOC, PT, and Severity
- NOCIs summary by SOC, PT and Relationship

In the summary tables, NOCIs will be presented by decreasing frequency of number of subjects with event and total events under “overall” treatment arm within each SOC and then similarly by decreasing frequency of number of subjects with event and total events under “overall” treatment arm within each PT.

All NOCIs collected during the follow-up period of the study will also be provided, for each treatment arm, study day, in duration, by severity and relationship to the treatment in by-subject listings.

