14.3.3.1.4	Summary of Overall Unsolicited Treatment Emergent Adverse Events by Treatment arm, from Day 1 to Day 29 Post-Vaccination.	Safety
14.3.3.1.5	Summary of duration (in days) of Overall Unsolicited Treatment Emergent Adverse Events by Treatment arm, from Day 1 to Day 29 Post-Vaccination	Safety
14.3.3.1.6.1	Summary of Unsolicited Treatment Emergent Adverse Events by System Organ Class, Preferred Term and Treatment arm, from Day 1 to Day 29 Post-Vaccination	Safety
14.3.3.1.6.2	Summary of Unsolicited Treatment Emergent Adverse Events by System Organ Class, Preferred Term, Severity and Treatment arm, from Day 1 to Day 29 Post-Vaccination	Safety

Table Number	Table Title	Population
14.3.3.1.6.3	Summary of Unsolicited Treatment Emergent Adverse Events by System Organ Class, Preferred Term, Relationship and Treatment arm, from Day 1 to Day 29 Post-Vaccination	Safety
14.3.3.1.7.1	Summary of Serious Adverse Events by System Organ Class, Preferred Term and Treatment arm, from Day 1 to Day 29 Post-Vaccination	Safety
14.3.3.1.7.2	Summary of Serious Adverse Events by System Organ Class, Preferred Term, Severity and Treatment arm, from Day 1 to Day 29 Post-Vaccination	Safety
14.3.3.1.7.3	Summary of Serious Adverse Events by System Organ Class, Preferred Term, Relationship and Treatment Arm, from Day 1 to Day 29 Post-Vaccination	Safety
14.3.3.1.7.4	Summary of Serious Adverse Events by System Organ Class, Preferred Term and Treatment Arm, From Day 30 to Day 365 Post-Vaccination	Safety
14.3.3.1.7.5	Summary of Serious Adverse Events by System Organ Class, Preferred Term, Severity and Treatment Arm, from Day 30 to Day 365 Post-Vaccination	Safety
14.3.3.1.7.6	Summary of Serious Adverse Events by System Organ Class, Preferred Term, Relationship and Treatment Arm, from Day 30 to Day 365 Post-Vaccination	Safety
14.3.3.1.8.1	Summary of New Onset of Chronic Illness by System Organ Class, Preferred Term and Treatment arm, from Day 1 to Day 29 Post-Vaccination	Safety
14.3.3.1.8.2	Summary of New Onset of Chronic Illness by System Organ Class, Preferred Term, Severity and Treatment arm, from Day 1 to Day 29 Post-Vaccination	Safety
14.3.3.1.8.3	Summary of New Onset of Chronic Illness by System Organ Class, Preferred Term, Relationship and Treatment Arm, from Day 1 to Day 29 Post-Vaccination	Safety
14.3.3.1.8.4	Summary of New Onset of Chronic Illness by System Organ Class, Preferred Term and Treatment Arm, from Day 30 to Day 365 Post-Vaccination	Safety

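### AE duration needs an end date and ongoing events get no value, so the planned duration table describes resolved events only and is biased short

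*SAP*

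**What the plan says.** The primary safety endpoint in SAP 2.3.1 reads "Frequency, duration, and severity of unsolicited treatment-emergent adverse events (TEAEs), serious AEs (SAEs" and continues to AESIs and NOCIs, through four weeks after the dose. SAP 2.3.2 names duration again for SAEs, AESIs and NOCIs through 12 months. Protocol version 2.0, sections 3.2.1 and 3.2.2, says the same.

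Five SAP rules bear on how duration is obtained and summarised:

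- SAP 3.2 gives one formula: "AE end date - onset of AE + 1".
- SAP 3.5 says: "No imputations will be made for missing or incomplete data unless otherwise stated". The four date rules that follow it only decide whether an event is a TEAE or a medication is concomitant. None supplies an end date.
- SAP 3.1 summarises continuous variables on the non-missing values.
- SAP 13.2 says "Missing unsolicited TEAE dates will be handled according to the rules determined in" section 3.1. The part of 3.1 it points to is a display convention that prints unknown date components as NK.
- SAP 13.2 also says "the duration of unsolicited TEAEs will be evaluated descriptively where subjects without AE are counted as missing". This deals with subjects who had no event, not with events that have not ended.

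The SAP does recognise ongoing events once. In SAP 3.2, study days "will be undefined for events that are 'Ongoing' at the end of the study". That sentence concerns study day; for duration the SAP is silent.

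The only duration table in SAP 18 is Table 14.3.3.1.5, "Summary of duration (in days) of Overall Unsolicited Treatment Emergent Adverse Events by Treatment arm", covering Day 1 to Day 29. For NOCIs, defined in SAP 13.4 as "a new medical condition which is chronic in nature", duration appears only in a by-subject listing.

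**The concern.** Taken together, these rules leave an ongoing event with no duration to summarise. A team following the SAP exactly would compute the mean, median and maximum in Table 14.3.3.1.5 from events that had ended. At any fixed cut, a long event is less likely to have ended than a short one, so the missing values are concentrated among the longest events. The table would understate how long unsolicited events last, and nothing in it would tell the reader how many events were left out.

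This is a named primary safety endpoint in a study whose safety results are purely descriptive, so the summary is itself the result. If no rule is set beforehand, the handling of ongoing events would be chosen during programming, possibly after unblinding.

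**Working it through.** The documents state no expected AE duration, no expected share of ongoing events and no interval to lock, so there is no figure of the plan's own to reproduce. The check has two parts.

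**1. A small example with the SAP formula.** Take three resolved events of 2, 3 and 5 days and one with onset on Day 10 still ongoing at a Day 29 cut. The SAP gives (2 + 3 + 5)/3 = 3.3 days with n = 3. The fourth event has lasted at least 29 − 10 + 1 = 20 days, so the mean over all four is at least (2 + 3 + 5 + 20)/4 = 7.5 days.

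**2. Size over a range.** Assumptions, none from the documents: onset is equally likely on each of Days 1 to 29; duration is exponential with parameter m, rounded up to whole days, and independent of onset; the SAP formula is applied to events that end by the cut.

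Let q = exp(−1/m). The true mean is μ = 1/(1 − q). An event with a days available from onset to the cut, both included, is ongoing with probability q^a. For a cut at Day 29, a runs from 1 to 29; for a cut at Day 59 it runs from 31 to 59. Then:

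- ongoing share: Ω = mean of q^a over the 29 onset days
- mean of resolved events = μ − A/(1 − Ω), where A = mean of a·q^a over the same days

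A is always positive, so the resolved-only mean is always too short.

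For m = 7 and a Day 29 cut: μ = 7.51; Ω = (1 − exp(−29/7))/(29 × (exp(1/7) − 1)) = 0.984/(29 × 0.1536) = 0.221; A = 1.557; resolved mean = 7.51 − 1.557/0.779 = 5.51 days. The shortfall is 2.00/7.51 = 27%.

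The same steps for m = 3, 7, 14 and 28:

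| True mean (days) | Ongoing, Day 29 cut | Resolved mean | Shortfall | Ongoing, Day 59 cut | Resolved mean | Shortfall |
|---|---|---|---|---|---|---|
| 3.5 | 8.7% | 3.2 | 10% | 0.0% | 3.5 | 0% |
| 7.5 | 22.1% | 5.5 | 27% | 0.3% | 7.4 | 2% |
| 14.5 | 40.7% | 7.4 | 49% | 4.8% | 12.5 | 14% |
| 28.5 | 61.2% | 8.7 | 69% | 21.0% | 17.2 | 40% |

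Counting ongoing events up to the cut as if they had ended is not a cure. With a true mean of 7.5 days and a Day 29 cut it gives 5.9 days, against 5.5 for resolved events only. It is a lower bound.

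**The case against.** **Silence is not exclusion.** No sentence removes ongoing events from the duration table, and the one rule on ongoing events concerns study day. The table shells are not in the text available here and could carry a row for ongoing events. That is fair, but the formula, the bar on imputation and the non-missing summaries leave no value to enter. SAP 13.2 does not repair this.

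**The Day 29 figures are a worst case.** The lock follows the Day 29 visit of the last of 76 subjects at about seven sites (SAP 2.1 and 16; protocol synopsis), so most subjects have later time in which to supply end dates. Protocol 9.5.1 asks that AEs be monitored until symptoms subside, and protocol 7.1.4 follows related AEs to resolution or stability. This stands, and it is why the Day 59 columns are shown. It reduces the bias without removing it: the last subjects enrolled have little extra time, and long events remain truncated.

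**A reader might infer that the vaccine will look better tolerated than it is.** The documents do not support that. One formula applies to both vaccine arms and placebo, and a distortion between arms would need durations that differ by arm, which nothing here shows. Ongoing events still count in the frequency, severity and relatedness tables and appear in the listings.

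**A reader might also infer that NOCI duration is undefined, or that a NOCI summary is biased.** That goes too far as well. A NOCI with a recorded end date has a duration, and no NOCI-specific duration summary is planned that could be biased. What is true is that most NOCI entries in the listing would probably be blank: with assumed mean durations of 1, 5 and 10 years and onset spread over Days 1 to 365, about 63%, 91% and 95% would have no end date by Day 365.

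**Conclusion.** The point holds for Table 14.3.3.1.5. Followed as written, the SAP reports the duration of resolved unsolicited TEAEs under a title that promises all of them, and the result is biased short. The direction needs only that longer events are less likely to have ended by the cut and that onset is unrelated to length. The size is an assumption throughout: about 10%, 27% and 49% for true means of 3.5, 7.5 and 14.5 days if each subject's events are cut at Day 29, and about 0%, 2% and 14% with 30 further days of end dates. For short events and a late lock it is close to nil.

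The consequence is confined to one descriptive safety summary. No test, sample size or event count is affected, and no bias between arms is established. For SAEs, AESIs and NOCIs the matter is one of presentation in the listings.

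**What to change.** In SAP 3.2 and 13.2, before unblinding:

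- State that an AE without an end date at the data cut is censored at the cut or at last contact, whichever is earlier.
- In Table 14.3.3.1.5, report the number and percent of events ongoing in each arm beside the duration statistics.
- Label those statistics as resolved events, or give a censoring-aware median. A Kaplan-Meier median is suitable only where event numbers allow; in arms of 16 to 30 subjects the count ongoing and a clear label may be enough.
- In the listings, show an ongoing event as lasting at least x days.
- For SAEs, AESIs and NOCIs still ongoing, add the same entry and the status at last contact to the existing listings. This should be in addition to duration: replacing it would change an endpoint named in the protocol.

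The cost is a few sentences and one changed table, with no new visits or assessments. Under the censoring-aware option the reported durations will be longer, and so less favourable, than the resolved-only figures.
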